3.2 Violations and Deviations

Protocol deviations are failures to adhere to the inclusion/exclusion criteria and protocol requirements and will be classified as major or minor protocol deviations.

Major protocol deviations will be identified and categorized by medical review before database lock for analysis.

The following deviations will be collected and reported:

- Informed consent violation
- Study treatment not taken/dispensed per protocol
- Concomitant medication, vitamins, minerals and/or supplements restriction violated
- Study procedure violated
- Visit deviation
- Adverse event (AE) reporting deviation
- Eligibility deviation
- Other deviation

4. STATISTICAL ANALYSIS

4.1 General Considerations

All data collected will be provided in listings, except data collected only for confirmation of study entry criteria and for study administrative purposes. If any participant is found to not have valid documented informed consent, that participant's data will be excluded from all study datasets, summaries, and listings, except as necessary to document the error.

Unless specified otherwise, the tables and listings for participant dispositions will be based on the Screened Set, all other TFLs will be based on FAS. TFLs will present results by treatment group (or cohort), visit and timepoint as applicable. The Trehalose treatment group labels used in analyses are displayed in Table 2. In addition, the historical control groups constructed in Section 4.2 will be included for comparison analysis between combined Trehalose group with historical control groups.

Table 2 Treatment Group Label

Treatment Group Label
Cohort 1 – Trehalose Naive
Cohort 2 – Platform Trial RGE Roll-over
Trehalose Total

All medical history and adverse events will be coded using Medical Dictionary for Regulatory Activities (MedDRA) 23.0; the primary system organ class (SOC) will be used for analyses. The medications will be coded using the World Health Organization (WHO) Drug Dictionary: WHODrug Global B3 September 1, 2020, a few medications not available in this version will be coded using WHODrug Global B3 March 1, 2023.

Except where specified otherwise, all continuous variables will be summarized with descriptive statistics (the number of non-missing values, mean, standard deviation (SD), median, lower quartile (Q1), upper quartile (Q3), minimum and maximum) and all categorical variables will be summarized with frequency counts and percentages in each category, by treatment group.

For conversion of days to years, months, or weeks, the following conversion factors will be used:

- 1 year = 365.25 days
- 1 month = 30.4375 days
- 1 week = 7 days

All analyses will be conducted using SAS version 9.4 or higher.

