3.0 GENERAL DESCRIPTION OF STUDY DESIGN

Planned enrolment is approximately 70 people living with ALS at up to 25 sites in the US. Participants will receive weekly 60- or 90-minute IV infusions of trehalose, 90.5 mg/mL, at a dose of 0.75g/kg at the

study center or at home. This is the same treatment dosage and dosing interval used in regimen E of the HEALEY ALS Platform Trial.

This EAP will enroll two cohorts of participants:

- Cohort 1: participants who do not qualify for any reasonably accessible ongoing clinical trials. This population represents a completely different patient population than that represented in the Platform Trial.
- Cohort 2: participants who have completed the Platform Trial Regimen E RCT and/or OLE and are not eligible for enrollment in another treatment regimen of the platform study. At the completion of their participation in the EAP, these participants may have been exposed to up to 76 weeks of IV trehalose – important long-term safety data.

Specifically, this EAP will capture safety, biomarker, and clinical efficacy data to augment the Phase 2/3 Platform Trial data of IV Trehalose.

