Regimen E screening will also be utilized for final analyses. TEAEs will be summarized by the number of events of a given classification experienced by participants in each cohort and treatment group and by the number and proportion of participants experiencing such an event in each cohort and treatment group. The number of events and proportion of participants experiencing TEAEs will be summarized without regard to MedDRA term for any TEAE, any serious TEAE, any severe TEAE, any related TEAE, and any TEAE leading to discontinuation of study drug. TEAEs will be summarized by MedDRA system organ class and preferred term for the following groups of TEAEs: all TEAEs, serious TEAEs, severe TEAEs, related TEAEs, and TEAEs leading to discontinuation of study drug. TEAEs and serious TEAEs will also be summarized by MedDRA system organ class and preferred term by cohort, treatment group, and time after randomization in the following intervals: 0 to 24 weeks (168 days), 24 to 48 weeks (336 days), and 48 to 72 weeks (504 days) or longer.

Clinical efficacy analyses (Aim 2): The median survival, decline of ALSFRS-R and SVC (in that order of priority) of IV trehalose treated EAP participants (Cohorts 1, 2) will be compared to predicted placebo progression using historical placebo controls. Such a historical placebo comparison group will be created using the pooled resource open access clinical trials (PRO-ACT) and the Natural History Consortium Study in ALS databases, which are available to the PIs will be used for completing these analyses. Propensity score stratification or model-based prediction approaches will be used for placebo control group creation from these databases. Both visual inspection and a time-to-event analysis (survival) or repeated measures analysis (ALSFRS-R and VC) will be used to compare the two groups.

For each participant in the EAP and historical control analysis data set, we will estimate their propensity score and calculate a propensity score stratification factor. Additionally, for each participant treated in the EAP, we will create a set of model-based predicted placebos. Each treated participant together with their model-based predictions will define a model-based stratification factor. Both propensity score and model-based prediction analyses will utilize a set of baseline covariates that are included in both the historical control database and the EAP.

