1.2 Study Design

This is an intermediate EAP trial to provide access to the investigational product, SLS-005, to participants with ALS who are not eligible to participate in clinical trials. Planned enrolment is approximately 70 people living with ALS at up to 25 sites in the US. Participants will receive weekly 60- or 90-minute IV infusions of trehalose, 90.5 mg/mL, at a dose of 0.75g/kg at the study center or at home. This is the same treatment dosage and dosing interval used in regimen E of the HEALEY ALS Platform Trial.

This EAP will enroll two cohorts of participants:

- Cohort 1: participants who do not qualify for any reasonably accessible ongoing clinical trials. This population represents a completely different participant population than that represented in the Platform Trial.
- Cohort 2: participants who have completed the Platform Trial Regimen E RCT and/or OLE and are not eligible for enrollment in another treatment regimen of the platform study. At the completion of their participation in the EAP, these participants may have been exposed to up to 76 weeks of IV trehalose – important long-term safety data.

Specifically, this EAP will capture safety, biomarker, and clinical efficacy data to augment the Phase 2/3 Platform Trial data of IV Trehalose.

Participants may be screened over and up to a 21-day period prior to treatment initiation. Participants who meet the inclusion criteria and none of the exclusionary criteria may be enrolled into the EAP. Participants may initiate treatment on the same day as the combined Screening/Baseline Visit, provided consent was obtained and all inclusion and exclusion criteria have been satisfied and eligibility has been confirmed by the investigator prior to treatment initiation.

Participants may receive up to 24 weeks of weekly infusions per protocol. There are up to 25 infusions over 24 weeks (first infusion occurs at the Screening/Baseline Visit). In addition to infusion visits, participants will have three scheduled in-clinic visits at Screening/Baseline, Week 3, and Week 24, and 1 phone call or telemedicine visits at Week 12 during the treatment period. The follow-up safety call will take place 28 +/- 7 days after the participant's last dose of the investigational medical product.

A Data and Safety Monitoring Board (DSMB) will be convened for safety monitoring of this research study. The DSMB Charter provides additional details.

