4.2.2 PS Estimation

PS method will be used to balance the population-level baseline characteristics between the Trehalose treated group and the eligible historical control analysis set. In order to calculate PS, the following selected common baseline demographics and characteristics variables of known prognostic significance will be used as covariates in PS estimation if applicable, other covariates may also be included.

- Age (years) [19]
- BMI (kg/m^2)
- Bulbar onset (Yes/No)
- Riluzole use (Yes/No)
- Time since ALS symptom onset (months) [19]
- Time since ALS diagnosis (months)
- Baseline ALSFRS-R total score
- Pre-baseline ALSFRS-R slope (points/month) [20]
- Baseline % predicted VC [21]

PS is the probability of a participant being assigned to a treatment instead of the other one conditional on a given set of baseline characteristics. It is determined by a logistic regression with all above common baseline covariates. To reduce any potential bias due to rare events, PS will be estimated using penalized maximum

likelihood estimation (PMLE) (Firth, 1993). The PS will be estimated for participants from Trehalose group and the eligible historical control analysis set. Overlap of PS between both groups will be assessed using standardized mean differences table and/or plot.

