4.7 Exploratory Endpoints Analyses

This section includes the clinical efficacy analyses on overall survival, decline of ALSFRS-R, % predicted SVC and ALSAQ-40 scores. All endpoints will be summarized descriptively for EAP study treatment cohorts and overall. The first three efficacy endpoints (overall survival, ALSFRS-R, % predicted SVC) will also compare the treatment effect between combined Trehalose group with the historical control groups under both FAS and PPS as appropriate.

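### Only the pooled cohorts are compared with historical controls, although roll-over participants may enter with up to 52 weeks of earlier trehalose already reflected in their propensity-score covariates

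*SAP*

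**What the plan says.** SAP 4.1 provides for a "comparison analysis between combined Trehalose group with historical control groups". SAP 4.7 states that OS, ALSFRS-R and % predicted SVC "will also compare the treatment effect between combined Trehalose group with the historical control groups", under FAS and PPS. Protocol 9.0 pools in the same way: "IV trehalose treated EAP participants (Cohorts 1, 2) will be compared to predicted placebo progression". By-cohort results are planned only within the EAP. SAP 4.10 lists no subgroup analyses. Cohort is not a constraint on the matching (SAP 4.2.3) or a term in the control-comparison models (SAP 4.7.1.2, 4.7.2.2, 4.7.3.2).

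The cohorts differ by design. Of Cohort 1, Protocol 3.0 says: "This population represents a completely different patient population than that represented in the Platform Trial". SAP 1.2 repeats this. That trial supplies Cohort 2, of whom Protocol 3.0 says that by the end of the EAP "these participants may have been exposed to up to 76 weeks of IV trehalose". Under Protocol 4.1, Cohort 2 must have completed the Regimen E RCT and the OLE, or the RCT alone where the site has no OLE.

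The propensity score (SAP 4.2.2) uses baseline ALSFRS-R, the pre-baseline ALSFRS-R slope and baseline % predicted VC, among others. SAP 4.1.1 sets baseline for treated participants as the last value before the first dose of study treatment, and for controls as the first study visit. SAP 4.4.2 computes the pre-baseline slope as 48 minus the baseline score, divided by months since onset. SAP 7 leaves Regimen E data out of the analysis.

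**The concern.** For a Cohort 2 participant who has already had trehalose, the months on drug fall inside the interval over which the pre-baseline slope is calculated. If the drug works, that slope is flatter than the untreated slope would have been, and the score pairs the participant with a control whose natural decline is slower. Part of the effect then disappears into the matching. The same reasoning applies to baseline score and VC.

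A second influence can run the other way. Cohort 2 had to survive and complete an earlier trial, while controls enter at their first study visit.

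One pooled number cannot separate these influences. It also averages people starting trehalose with people continuing it, so it does not answer either question cleanly. SAP 4.2 introduces the controls in order to estimate the treatment effect, so what the estimate refers to matters.

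**Working it through.** **The plan's own figure.** The documents give no effect size or power for this comparison. Their power figures concern NfL and are not in dispute. The relevant figure is the 76-week maximum exposure. Subtracting the 24 EAP weeks gives 76 − 24 = 52 weeks before EAP baseline, or 52 × 7 / 30.4375 = 12.0 months.

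**Assumptions, not in the documents.** Time from onset to first trehalose, t0, is 15, 20 or 30 months. Prior exposure, tt, is 0, 24 weeks (5.5 months) or the 52-week maximum. Cohort 2 is 25–75% of participants. Each person's slope is stable, and matching on pre-baseline slope is exact.

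**Formula.** Let b be the untreated monthly decline and e the fraction by which trehalose slows it.

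- Pre-baseline slope: [b·t0 + b(1−e)·tt] / (t0+tt) = b[1 − e·tt/(t0+tt)]. An exactly matched control goes on declining at this rate.
- The treated participant declines at b(1−e), so the observed difference is b·e[1 − tt/(t0+tt)] against a true b·e.
- Share lost: tt/(t0+tt). Both b and e cancel.

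Example with b = 1, e = 0.3, t0 = 15, tt = 12: the pre-baseline slope is (15 + 0.7 × 12)/27 = 0.867. The observed difference is 0.867 − 0.700 = 0.167 against a true 0.300, a loss of 44%.

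| t0 (months) | tt = 0 | tt = 5.5 months | tt = 12.0 months |
|---|---|---|---|
| 15 | 0% | 5.5/20.5 = 26.8% | 12.0/27.0 = 44.4% |
| 20 | 0% | 5.5/25.5 = 21.6% | 12.0/32.0 = 37.5% |
| 30 | 0% | 5.5/35.5 = 15.5% | 12.0/42.0 = 28.6% |

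These are losses within Cohort 2. The pooled loss is this share times the Cohort 2 fraction. At most it is 0.75 × 44.4% = 33%. With a 25% fraction and 52 weeks it is 0.25 × 44.4% = 11%. With naive roll-overs it is zero.

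**Simulation check.** Nearest-neighbour matching was run on baseline score, pre-baseline slope and time since onset. It assumed 30% slowing, a mean decline of 1 point/month, 52 weeks of prior trehalose throughout Cohort 2, and a mean of 24–48 months from onset to EAP baseline.

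- Cohort 1 alone recovered the true effect to within 0.06 points in every setting.
- Cohort 2 alone retained 46% (0.68 of 1.48 points, 24 months) to 69% (0.77 of 1.11, 48 months) with stable slopes. It retained about 64–84% when past and future slopes correlated at 0.6.
- The pooled comparison retained 58–92% with stable slopes and 76–96% at correlation 0.6.
- With no true effect, the bias was zero apart from simulation noise.

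The largest simulated pooled loss (42%) exceeds 33% mainly because the 24-month case leaves only about 12 months before first trehalose, outside the 15–30 range. The simulation covers neither OS, VC nor selection through Regimen E.

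**The case against.** The strongest reply is that SAP 2 describes all analyses as descriptive, with no formal hypothesis testing and with unadjusted, exploratory p-values. The stated objective is progression in a broad population, and pooling was specified in the protocol. This limits how serious the point is but does not remove it. SAP 4.7.1.2 calls the OS result statistically significant at p < 0.05, and SAP 1 foresees possible use in a regulatory submission.

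Three stronger readings are tempting, and the documents do not support them.

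- *The controls are untreated.* The SAP version history says the external database includes people on ALS medication and that all available data will be used. Riluzole use is itself a score covariate. The controls are better described as not treated with trehalose.
- *All roll-overs are pre-treated.* Protocol 4.1 admits RCT completers at sites without an OLE, and Protocol 1.3.3 describes ALS patients receiving SLS-005 or placebo. Some of Cohort 2 may therefore be naive, and 52 weeks is a maximum.
- *The pooled result is biased toward no effect.* Selection may pull the other way. It is also partly offset: the score includes time since onset, time since diagnosis and baseline ALSFRS-R, and SAP 4.2.1 requires controls to have a post-baseline ALSFRS-R and/or VC, so they too are selected on remaining under observation.

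It is also fair to say that the plan matches within a caliper on a score from at least nine covariates, not exactly on slope. Where slope is balanced less closely, or past slope predicts future slope less well, the loss is smaller.

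**Conclusion.** The point holds in a limited form. For Cohort 2 participants with earlier trehalose, the propensity score adjusts for variables that treatment may have changed. The plan has no cohort-specific comparison with controls that would show the consequence. The pooled estimate mixes starting with continuing treatment, and the net direction of bias is uncertain.

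The illustrative loss is 0–44% of the ALSFRS-R slope effect in Cohort 2 and 0–33% pooled. A reader might take the 44% as the bias in the planned analysis. It is not: it applies only within Cohort 2, at the maximum exposure, the shortest assumed time from onset and exact matching. The documents give neither the cohort split nor time since onset. Without a true effect, nothing is lost through matching. For OS and VC the concern is one of principle and has not been sized. The change should be made, but the pooled analysis need not be withdrawn.

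**What to change.** Add to SAP 4.7 a Cohort 1-only sensitivity comparison with historical controls for OS, ALSFRS-R and % predicted VC, re-estimating the score and re-matching within Cohort 1. If matched-pair strata lack events in the OS analysis, use the unstratified hazard ratio and log-rank test that SAP 4.7.1.4 already provides (there listed under PPS).

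Report this beside the retained pooled result. State that any reading as the effect of starting trehalose rests on Cohort 1. Note its own limit: the life-expectancy criterion of at least 6 months in Protocol 4.1 applies to Cohort 1 and is not among the criteria applied to controls in SAP 4.2.1.

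Show any Cohort 2 comparison with controls as descriptive only, with the caveat that its covariates may be measured after treatment. Re-anchoring Cohort 2 to a pre-trehalose baseline would need the Regimen E data that SAP 7 leaves out.

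The cost is a wider interval for Cohort 1, possible instability of a nine-covariate score in part of a sample of about 70, and one extra set of programs and tables. No new data are needed.

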4.1.1 Definitions, Derivations and Classifications

Definition of Baseline

The baseline value for all endpoints (i.e., laboratory parameters and vital signs) will be the last available value prior to the first dose of study treatment in Trehalose group, and the date of first study visit in historical control group.

Assessments taken on the same day as study treatment will be assumed to be before study treatment unless indicated to be obtained post-study treatment.

Definition of Day 1

Study Day 1 is defined as the first day of study treatment in Trehalose group, and the date of first study visit in historical control group. This will also be considered the reference start date.

Definition of Study Day

Study Day will be computed as follows:

- Study Day = (Date of event – Date of study day 1) + 1 if the date of the event is on or after the date of study day 1.
- Study Day = (Date of event – Date of study day 1) if the date of the event is prior to the date of the study day 1.

Derivations Involving Dates

The number of days between two dates, the date of interest and the reference date, will be calculated as (Date of event – Reference date) + 1 when the event date is on or after the reference date; or, as (Reference date – Date of event) + 1 when the event date is before the reference date. The resulting value is then converted to years, months, or weeks, as appropriate. Partial dates will be imputed before calculating the number of days (See Appendix 2 for partial or unknown date imputation rules).

Common Calculations

Change from baseline (CHG) will be calculated as:

$$\text{Change from baseline} = \text{Actual (observed) value at post baseline visit} - \text{baseline value}$$

Percent change from baseline (PCHG) will be calculated as:

$$\text{Percent change from baseline (\%)} = 100 * (\text{Change from baseline at post baseline visit} / \text{Baseline value})$$

If baseline is not available, the change from baseline and percent change from baseline will not be calculated and will remain missing.

Demographics

Age in years at time of enrollment is not collected in eCRF and will be derived relative to the date of informed consent as: (informed consent date – date of birth + 1) / 365.25 and truncated to 1 decimal point. Age in years at time of first study treatment administration will be derived for participants treated and used for analysis summary. It will be calculated as (date of first study treatment – date of birth + 1) / 365.25 and truncated to 1 decimal point.

Body mass index (BMI) in kg/m² will be calculated as by weight in kilograms (kg) divided by height in meters squared (i.e., weight / [height*height]).

4.1.2 Windowing, Unscheduled Visits and Repeat Test Results

All assessments collected at scheduled and unscheduled visits will be included in the by-participant data listings.

For Safety endpoints, the data will be analyzed according to the nominal visits except Baseline which is defined as last available value prior to the first dose of study treatment. The results collected at scheduled visits per

protocol will be included in the by-visit summary tables. For laboratory data analysis at the scheduled visits, central-laboratory values will (preferentially) be selected for a given visit; however, if there is no non-missing central-laboratory value available and there is a non-missing local-laboratory value collected at the visit, then a local-laboratory value will be used.

In addition, for Safety endpoints of laboratory data, vital signs and C-SSRS assessments, the last assessment during the post-baseline period will also be summarized using the analysis visit name “End of Treatment Period”, which is defined as the last measurement from all post-baseline visits including the unscheduled visits and early termination visit.

For Efficacy and Biomarker endpoints, the protocol defined visit windowing in Table 3 will be used to window the unscheduled visits or early termination visit to scheduled visit when it doesn’t exist. If unscheduled visits or early termination assessments fall in the same window, then select the assessment closest to the target assessment day. If there are two assessments that fall into a visit window and are equidistant from the target assessment day, then the later assessment will be selected.

Table 3 Analysis Visit Windows for Efficacy (ALSF-R, SVC, ALSAQ-40) and Biomarker

Analysis Visit	Nominal Day	Lower Limit	Upper Limit
Baseline	1	None	Time of first dose of study treatment
Week 3	22	19	25
Week 12	85	78	92
Week 24	169	155	183

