6.6.3 Clinical Safety Laboratory Assessments

The investigator or designee should review the laboratory report(s) and monitor CBC with differential, complete chemistry panel, Hb A1C, and urinalysis and notify the medical monitor of any clinically relevant changes resulting in a treatment emergent serious adverse event (TESAE). Clinically significant abnormal laboratory findings are those which are not associated with the underlying disease, unless judged by the Investigator or designee to be more severe than expected for the participant's condition.

All laboratory tests with values considered clinically significantly abnormal during participation in the EAP should be repeated, at the investigator's discretion, until the values return to normal or baseline or are no longer considered clinically significant. If such values do not return to normal/baseline within a period of time judged reasonable by the investigator or designee, the etiology should be considered, and the medical monitor consulted. As needed, clinical safety labs may be drawn at the study site or obtained at a local site convenient for the participant.

Serum pregnancy testing must be performed on all WOCBP at Screening/Baseline. Pregnancy tests may also be performed at any time during the protocol at the investigator's discretion. A negative serum pregnancy test is required for WOCBP before SLS-005 initial administration.

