6.7.8 Overdose

Certain safety events that occur in association with investigational product may require reporting. These safety events include, but are not limited to, the following:

- Overdose of the investigational product, where 'overdose' is defined as > 125% of the intended dose for a single treatment day infusion.
- Suspected abuse/misuse of the investigational product
- Inadvertent or accidental exposure to the investigational product
- Medication error involving study drug (with or without participant exposure to the investigational product, e.g., name confusion)
- The half-life of SLS-005 is approximately 1.5 hours, and there is no antidote. SLS-005 is metabolized to 2 glucose molecules, there are no other metabolites. Supportive care with monitoring of vital signs, blood glucose levels, and liver enzymes should be considered. In 1 subject who received 81 g of SLS-005, there was an increase in liver enzyme levels, but liver function remained normal and liver enzyme values returned to normal without treatment.

Safety events associated with an AE/SAE should also be reported in the EDC system. The SI should also contact the Medical Monitor within 24 hours of the SI's awareness.

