4.9.3 Laboratory Data

Clinical laboratory data includes the measurements of lab parameters from hematology (including HgbA1C), chemistry, urinalysis and serum pregnancy collected from both central laboratory and local laboratory.

- Laboratory data in summary tables and participant data listings will be presented in the International System of Units (SI units; Système International d'Unités).
- If the same lab test has measurements from both central and local labs at same time point, the one from central lab will be used for analysis in tabulation summary.
- Given the lab measurements' baseline and post-baseline results are collected from different labs (most baseline lab measurements are completed at local labs while most Week 24 lab measurements are collected at central lab), the lab results will not be compared with baseline to investigate the change from baseline trend over time except HgbA1C (%). The HgbA1C is a significant parameter as a measure of diabetes, the change from baseline will be calculated and presented in table.
- All scheduled hematology and chemistry parameters' normality assessments will be summarized by visit for each treatment cohort and overall. The assessments will be classified "Normal", "High" and "Low" with respect to the parameter-specific reference ranges established in central lab; and classified as "Normal" and "Abnormal" (with "clinically significant" information) compared to reference ranges by investigator in local lab. The local labs don't collect reference ranges in eCRF, then the status of "High" or "Low" can't be derived programmatically for measurements from local lab, so the summary will be a mixture of assessment values from both central lab and local labs. The number and percentage of participants in each assessment category will be provided.
- All laboratory data will be presented in participant data listings with normality assessments included. The laboratory measurements identified as abnormal (ie, outside the normal range) will also be listed separately by participant, laboratory category, lab parameters at relevant time points.

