4.9.5.3 C-SSRS Assessment

The most severe suicidal ideation and most severe suicidal behavior will be summarized descriptively by visit for each treatment cohort and overall under FAS. In addition, the most severe assessments during the treatment period for suicidal ideation and suicidal behavior will be summarized as well, according to the table below which list the ideation and behavior from most severe to least severe.

Suicidal Ideation Severity	Suicidal Behavior Severity

 • Active suicidal ideation with specific plan and intent • Active suicidal ideation with some intent to act, without specific plan • Active suicidal ideation with any methods (not plan) without intent to act • Non-specific active suicidal thoughts 	
 • Completed suicide • Actual attempt • Interrupted attempt • Aborted attempt

Suicidal Ideation Severity	Suicidal Behavior Severity
• Wish to be dead	• Preparatory acts or behavior

All the C-SSRS assessment information collected will be provided in the data listing.

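### The laboratory tables have no worst-value or any-time-abnormal summary, so a resolved abnormality found at an unscheduled draw is in no laboratory table

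*SAP*

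**What the plan says.** SAP 4.1.2 analyses safety data by nominal visit. Results from visits scheduled per "protocol will be included in the by-visit summary tables". Unscheduled results have two destinations. The first is the listings: "All assessments collected at scheduled and unscheduled visits will be included in the by-participant data listings". The second is the *End of Treatment Period* row for laboratory data, vital signs and C-SSRS, "which is defined as the last measurement from all post-baseline visits including the unscheduled visits and early termination visit".

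SAP 4.9.3 then specifies the main laboratory table: "All scheduled hematology and chemistry parameters' normality assessments will be summarized by visit for each treatment cohort and overall". It names hematology and chemistry, not urinalysis. Change from baseline is planned only for HbA1c, because most baseline results are local and most Week 24 results are central. Abnormal values get a separate listing.

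The Schedule of Activities places safety laboratory draws at Screening/Baseline, Week 3 and Week 24. Protocol 6.6.3 says that clinically significant abnormal values "should be repeated, at the investigator's discretion, until the values return to normal or baseline or are no longer considered clinically significant".

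For C-SSRS the SAP does more (4.9.5.3): "the most severe assessments during the treatment period for suicidal ideation and suicidal behavior will be summarized as well". Nothing equivalent is written for laboratory data.

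**The concern.** With two scheduled post-baseline draws in 24 weeks, much of what is learned about a transient laboratory change may come from unscheduled tests. The SAP lets such a test into a laboratory table only if it is the participant's last post-baseline value. A value that rose and then fell back between visits adds nothing to the laboratory tables, and the participant can look normal in every row.

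The documents give reason to care about this pattern. Protocol 6.7.8 describes a participant given 81 g in whom "there was an increase in liver enzyme levels, but liver function remained normal and liver enzyme values returned to normal without treatment"; Protocol 1.3.3 calls that event possibly related and says it was reported as a SUSAR. Urine glucose was the most common adverse event in the OPMD study (52% of patients) and in the SCA3 study (20%, n=3). SAP Table 1 names clinical laboratory tests as a safety assessment alongside TEAEs. A reader of the laboratory tables alone could conclude that there was no transient signal when the tables were not built to show one.

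**Working it through.** The plan states no figure on this point, so the check is mainly a reading of the rules side by side.

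**Step 1: time between scheduled draws.** Inputs from the Schedule of Activities: Week 3 is Day 21 ±3 and Week 24 is Day 168 ±14.
- Nominal gap: 168 − 21 = 147 days; 147/168 = 87.5% of the treatment period.
- Shortest gap within the windows: 154 − 24 = 130 days.
- Longest gap within the windows: 182 − 18 = 164 days.

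**Step 2: where a hematology or chemistry abnormality goes.** Protocol 10.3.1 makes a clinically significant (CS) abnormal laboratory finding an adverse event. SAP 4.9.2 counts any adverse event with onset or worsening on or after first dose, whatever the visit.

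| Abnormal value after first dose | By-visit row | End of Treatment row | TEAE tables | Listings |
|---|---|---|---|---|
| At scheduled Week 3 or Week 24 | Yes | Only if last value | If CS | Yes |
| Unscheduled, and the last post-baseline value | No | Yes | If CS | Yes |
| Unscheduled, later resolved, judged CS | No | No (later value shown) | Yes | Yes |
| Unscheduled, later resolved, not judged CS | No | No (later value shown) | No | Yes |

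The last two lines are the gap. As an illustration, suppose a liver enzyme is raised at an unscheduled Week 9 draw and normal at Week 11 and at a final Week 24 draw. If the other scheduled results are normal, every row of the laboratory tables shows normal. Whether the participant is counted anywhere then depends on the investigator's judgement of significance.

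**Step 3: whether the TEAE route fully covers the gap.** Protocol 10.3.1 leaves clinical significance to the site investigator, at up to 25 sites. Protocol 6.6.3 adds a filter: findings associated with the underlying disease do not count unless judged more severe than expected. Protocol 1.3.3 shows how uneven this can be. In the OPMD study, glycosuria as an adverse event came from one site only, where the investigator judged the results clinically significant although the patients were asymptomatic. TEAE counts of a laboratory finding can therefore reflect site practice as well as incidence.

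**Step 4: whether another summary could be built.** SAP 4.9.3 classifies central results as Normal, High or Low, and local results as Normal or Abnormal with clinical-significance information. Combining High and Low gives a common Normal/Abnormal scale, so an any-time-abnormal count is feasible from the planned data.

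**The case against.** The strongest reply is that clinically significant abnormalities are not lost. They are adverse events, and SAP 4.9.2 tabulates TEAEs with numbers and percentages by system organ class and preferred term, by maximum severity and by time to onset. Both known signals, the liver-enzyme rise and the urine glucose, surfaced through adverse event reporting, and this plan keeps that route. Every abnormal value is also listed, for a study of about 70 participants; the Medical Monitor reviews abnormal laboratory results (Protocol 10.5); a DSMB is convened; and the analyses are descriptive. All of this stands, and it keeps the point minor. It does not supply an incidence for abnormalities that were not judged clinically significant.

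Four stronger readings are tempting and are not supported.
- A reader might infer that such an abnormality appears in no summary at all. The TEAE tables contradict that for clinically significant values.
- A reader might infer that abnormal values are repeated until normal, so that the last value is always a recovered one. Protocol 6.6.3 leaves repeats to the investigator's discretion and lets them stop at baseline or when the value is no longer clinically significant. For a participant whose last test is the Week 24 draw, the last value is simply that draw. Repeats do not replace a scheduled result in the by-visit rows.
- A reader might turn the 87.5% into a share of abnormalities that the SAP hides. It describes the visit schedule. Any such share would need assumed onset times and durations, and would include abnormalities never detected, which no table could recover.
- A reader might infer that urinalysis is not summarised anywhere. Only the normality table is limited to hematology and chemistry. SAP 4.1.2 speaks of laboratory data generally, and the table shells are in a separate Data Presentation Plan that was not available.

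**Conclusion.** The point holds in limited form. Neither SAP 4.1.2 nor 4.9.3 provides a worst-post-baseline or any-time-abnormal laboratory summary. A resolved abnormality from an unscheduled draw is missing from every laboratory table, and one not judged clinically significant has no incidence anywhere. The normality table as written also omits urinalysis, which covers the finding most often reported as an adverse event in the earlier OPMD and SCA3 studies.

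The number of participants affected cannot be estimated, because the documents do not give the frequency of unscheduled draws or of transient abnormalities. The 147-day interval shows only that there is room for such events. The conclusion assumes that the by-visit tables exclude unscheduled results. SAP 4.1.2 does not use the word only, but its separate allocation of unscheduled values to the listings and the last-value row leaves no other reading. Severity is minor: a cheap improvement to the presentation of safety data.

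**What to change.** In SAP 4.1.2 and 4.9.3, add one participant-level table over all scheduled, unscheduled and early-termination post-baseline results. It should give, by cohort and overall, the number and percentage of participants with any abnormal value for liver enzymes, bilirubin, glucose and urine glucose.

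- Combine central High and Low into Abnormal so that central and local results can be pooled.
- Show clinical significance only where it was recorded; SAP 4.9.3 describes it for local assessments.
- Relabel the *End of Treatment Period* row as last available value, so that it is not read as a summary of the whole period.

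The cost is SAP wording and one extra table from data already collected. The table will show more abnormalities than the by-visit rows and will partly overlap the TEAE tables; a footnote can say so.
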